### 6.12.4 Secondary Endpoints

#### 6.12.4.1 Change in pure tone audiometry (average of the hearing threshold of the 2 most affected hearing frequencies identified at study entry) in affected ear from baseline to the end of treatment visit (Visit D28± 3)

Mean changes from baseline in pure tone audiometry (average of the hearing threshold of the 2 most affected hearing frequencies identified at baseline) on pure tone audiometric air conduction testing in affected ear will be analyzed using the same modeling approach as for the primary endpoint for both study parts. The 2 most affected hearing frequencies will be defined as the first 2 frequencies within the 3 most affected hearing frequencies identified at baseline sorted by descending order of the hearing losses observed at baseline and by increasing order of the frequencies.

	Sponsor:	Sensorion
	Protocol Number:	SENS 401-201
STATISTICAL ANALYSIS PLAN, PHASE 2-3-4		

Values at each timepoint and their changes from baseline will also be summarized descriptively by treatment group and a line plot of the model estimates of the mean changes from baseline over time by treatment group will be presented.

***6.12.4.2 Change in pure tone audiometry (the most affected hearing frequency identified at study entry) in affected ear from baseline to the end of treatment visit (Visit D28± 3)***

Mean changes from baseline in pure tone audiometry (the most affected hearing frequency identified at baseline) on pure tone audiometric air conduction testing in affected ear will be analyzed using the same modeling approach as for the primary endpoint for both study parts but without imputation for missing Day 28 results. The most affected hearing frequency will be defined as the first frequency within the 3 most affected hearing frequencies identified at baseline sorted by descending order of the hearing losses observed at baseline and by increasing order of the frequencies.

Values at each timepoint and their changes from baseline will also be summarized descriptively by treatment group and a line plot of the model estimates of the mean changes from baseline over time by treatment group will be presented.

***6.12.4.3 Change in pure tone audiometry (PTA; average of the hearing threshold of 3 contiguous most affected hearing frequencies in decibels as identified at study entry on pure tone audiometric air conduction testing) in affected ear from baseline to the end of study visit (Visit D84 ± 3)***

Mean changes from baseline in pure tone audiometry (average of the hearing threshold of the 3 contiguous most affected hearing frequencies identified at baseline) on pure tone audiometric air conduction testing in affected ear will be analyzed using the same modeling approach as for the primary endpoint for both study parts and expanded by including the Day 84 data in the model.

Values at each timepoint and their changes from baseline will also be summarized descriptively by treatment group and a line plot of the model estimates of the mean changes from baseline.

***6.12.4.4 Change in speech discrimination threshold from baseline to Day 28, and 84.***

The Speech recognition threshold is the minimum hearing level at which the patient can correctly recognizes the speech stimuli 50% of the presented speech material. Assessments with missing value with "Reason not performed" = "No response due to hearing loss" will be assigned with the maximum observed value in the database.

	Sponsor:	Sensorion
	Protocol Number:	SENS 401-201
STATISTICAL ANALYSIS PLAN. PHASE 2-3-4		

Mean changes from baseline of the speech recognition threshold at Days 7, 14, 28 and 84 will be analyzed using the same modeling approach as for the primary endpoint for both study parts. A line plot will be produced to show the discrimination threshold by timepoint for each treatment group for all individual subjects.

**6.12.4.5 Frequency and severity of tinnitus at Days 7, 14, 28, and 84 assessed by numerical rating scale**

Mean changes from baseline of the severity of tinnitus (assessed numerical rating scale) at Days 7, 14, 28 and 84 will be analyzed using the same modeling approach as for the primary endpoint. For Days 7 and 14 the patients diary log data (PM measurements) will be used.

For each relevant timepoint the number and percentage of patients experiencing tinnitus will be tabulated. Severity of reported tinnitus will be summarized as counts and percentages as well on a scale from 0 (no tinnitus) to 10 (extreme tinnitus).

All data on reported tinnitus occurrences and severity will also be listed.

**6.12.5 Exploratory Endpoints**

All the following endpoints will only be analyzed based on the ITT population. The results will be presented descriptively (with confidence intervals where indicated, 90% confidence intervals for Part 1 data, 95% confidence intervals for Part 2 data).

**6.12.5.1 % of patients with complete hearing recovery defined as PTA <20 dB or hearing similar to the unaffected contralateral ear**

The proportion of patients with a complete hearing recovery or hearing similar to the unaffected ear will be summarized at Day 28 and Day 84 alongside an exact confidence interval. Hearing in the affected ear will be considered similar to the unaffected one if the absolute difference in pure tone audiometric air conduction testing (average of the hearing threshold of 3 contiguous most affected hearing frequencies in decibels as identified at study entry) is < 5dB, and this rule will also be applied to cases where either an old audiogram was used or normative values were considered as reference (e.g. pre-existing contralateral hearing loss with no audiogram in the past 2 years). Patients with complete hearing recovery are those that have pure tone audiometric air conduction testing (average of the hearing threshold of 3 contiguous most affected hearing frequencies in decibels as identified at study entry) of < 20dB.

	Sponsor:	Sensorion
	Protocol Number:	SENS 401-201
STATISTICAL ANALYSIS PLAN. PHASE 2-3-4		

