#### 6.2.3 Exploratory efficacy endpoints

- % of patients with complete hearing recovery defined as PTA <20 dB
- % of patients with marked improvement defined as PTA absolute improvement > 30 dB
- % of patients with air PTA > 35 dB and > 90 dB on Day 7, Day 14 and end of study visit (visit D84± 3).
- Change in PTA from baseline to Day 7, Day 14 and end of study visit (Visit D84± 3).
- % of responders (response is defined as an improvement of 10dB or more in PTA).
- Word recognition score at 80 dB and 60 dB in the affected ear on Day 28 and 84.
- Relationship between time of onset of symptoms to first study drug intake and the primary endpoint
- Frequency and severity of any vertigo at days 7, 14, 28 and 84

- Tinnitus burden based on the change in tinnitus QOL scores at days 7, 14, 28 and 84
- Change in biomarkers
- Change in EQ-5D-5L scores between baseline and Day 28 and 84.
- Change in DPOAE at Days 7, 14, 28, and 84 compared to baseline values
- Change in TEOAE at Days 7, 14, 28 and 84 compared to baseline values

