### 3.3 Exploratory Efficacy Endpoints

- % of patients with complete hearing recovery defined as PTA <20 dB or hearing similar to the unaffected contralateral ear
- % of patients with marked improvement defined as PTA threshold absolute improvement > 30 dB
- % of patients with PTA > 35 dB and > 90 dB on Day 7, Day 14 and end of study visit (visit D84± 3)
- % of responders (response is defined as an improvement of 10dB or more) in PTA
- Word recognition score at 80 dB and 60 dB in the affected ear on Day 28 and 84
- Relationship between time of onset of symptoms to first study drug intake and the primary endpoint
- Frequency and severity of any vertigo at day 1,7,14, 28 and 84
- Tinnitus burden based on the change in tinnitus QOL scores at day 1,7,14, 28 and 84

	Sponsor:	Sensorion
	Protocol Number:	SENS 401-201
STATISTICAL ANALYSIS PLAN. PHASE 2-3-4		

- Change in biomarkers
- Change in EQ-5D-5L scores between baseline and Day 28 and 84
- Change in Distortion Products Otoacoustic Emissions (DPOAE) at Days 7, 14, 28, and 84 compared to baseline values
- Change in Transient Evoked Otoacoustic Emissions (TEOAE) at Days 7, 14, 28 and 84 compared to baseline values

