### 6.12.1 Primary Endpoint

The primary endpoint is the change in pure tone audiometry (PTA: average of the hearing threshold of 3 contiguous most affected hearing frequencies in decibels as identified at study entry) on pure tone audiometric air conduction testing in the affected ear from baseline to the end of treatment visit (Visit D28 ± 3).

The 3 most affected contiguous audiometric test frequencies are defined with respect to the unaffected contralateral ear and will be fixed for all further calculations. In case of a pre-existing contralateral hearing loss, the corresponding values of a pre-existing audiogram of the affected ear, if dating back less than 2 years, will be considered as the reference. For all other scenarios (e.g. pre-existing contralateral hearing loss with no audiogram in the past 2 years) the reference frequencies will be set using the ISO 7029;2017 norm values. In case of bilateral acute acoustic trauma leading to sudden sensorineural hearing loss, the most affected ear according to the inclusion criteria will be considered. If both ears are equally affected, the right ear will be considered.

At baseline, if 2 or more sequences of 3 contiguous frequencies are similarly affected, the index sequence with the lower contiguous frequencies will be selected as the reference. Pure tone average frequencies determined at baseline will remain fixed for all evaluations.

If one of the frequencies is missing for post baseline values the PTA will be averaged on 2 out of the 3 identified frequencies. If more than 1 is missing, the PTA will not be calculated.

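### The similar-hearing limb of the exploratory recovery endpoint is two-sided, so an affected ear at 20 dB or above that ends 5 dB or more better than its reference counts as not recovered

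*SAP*

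**What the plan says.** The endpoint has two alternative limbs. The heading of SAP 6.12.5.1 gives "complete hearing recovery defined as PTA <20 dB or hearing similar to the unaffected contralateral ear", and SAP 3.3 and the protocol synopsis agree. Protocol 6.2.3 has the first limb only: "of patients with complete hearing recovery defined as PTA <20 dB".

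The SAP then defines similarity: "Hearing in the affected ear will be considered similar to the unaffected one if the absolute difference in pure tone audiometric air conduction testing", taken over the three index frequencies, "is < 5dB, and this rule will also be applied to cases where either an old audiogram was used or normative values" serve as the reference. Both limbs feed one figure: "The proportion of patients with a complete hearing recovery or hearing similar to the unaffected ear will be summarized at Day 28 and Day 84", with an exact confidence interval.

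SAP 6.12.1 sets the reference. It is normally the other ear. If that ear already had a hearing loss, it is an audiogram of the affected ear less than two years old. In all remaining cases "the reference frequencies will be set using the ISO 7029;2017 norm values". No dB level is given for what counts as an existing loss in the other ear.

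**The concern.** A lower PTA is better hearing, so a recovery rule should never turn a recovery into a failure because the affected ear hears better. A modulus does that: it treats an ear 5 dB better than its reference exactly like one 5 dB worse.

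The similarity limb changes the classification only for patients at 20 dB or above, that is, those whose reference is itself raised. The flaw therefore falls on the patients the limb was added to serve. Such patients can enter the trial:

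- Protocol 8.1 sets no upper age limit, and Protocol 5.1 gives the highest incidence at 65 and over.
- Protocol 8.2 excludes known asymmetry only above 20 dB, so the affected ear may have been the better one before onset.
- Under Protocol 10.1.1 the final threshold search moves in 5 dB steps, and retest agreement within 5 dB counts as reliable. One step at each of the three index frequencies is enough to put a recovered ear exactly 5 dB better, which fails.

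At stake is the accuracy of a descriptive recovery proportion, not a test result.

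**Working it through.** The plan gives no expected recovery rate or sample size for this endpoint, so there is no figure to reproduce. The check is of the rule itself.

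**Inputs.** A is affected-ear PTA and R is reference PTA. The 20 dB and 5 dB cut-offs and the either-or structure come from SAP 6.12.5.1.

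**Rule as written.** Recovered if A < 20 or |A − R| < 5.

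**Where a better ear fails.** Being at least 5 dB better means R − A ≥ 5, so the second limb fails. The first limb fails when A ≥ 20. Together, R ≥ A + 5 ≥ 25.

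**Worked case, R = 30 dB.**

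| A (dB) | A − R | As written | With A < 20 or A − R < 5 |
|---|---|---|---|
| 19 | −11 | recovered (first limb) | recovered |
| 20 | −10 | not recovered | recovered |
| 22 | −8 | not recovered | recovered |
| 25 | −5 | not recovered | recovered |
| 26 | −4 | recovered | recovered |
| 30 | 0 | recovered | recovered |
| 34 | +4 | recovered | recovered |
| 35 | +5 | not recovered | not recovered |

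As hearing improves from 35 to 19 dB, the written rule goes from failure to recovery, back to failure, and back to recovery. The signed rule changes once.

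**All combinations.** The mean of three thresholds measured in 5 dB steps moves in steps of 5/3 dB. Over −10 to 120 dB (an assumed range) that gives 79 values per ear.

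- Pairs with the affected ear at least 5 dB (three steps) better: 76 × 77 / 2 = 2926.
- Of these, pairs with A ≥ 20 dB: 58 × 59 / 2 = 1711. All are not recovered as written, and all have R ≥ 25 dB.
- The other 2926 − 1711 = 1215 have A < 20 dB and are recovered through the first limb.

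These are counts of possible values, not of patients.

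**Scale.** One patient is 1/37 = 2.7 percentage points in a Part 1 arm and 1/95 = 1.1 points in a Part 2 arm. As an illustration only, suppose a fully recovered ear differs from its reference by a normal deviate with mean 0. The chance of being at least 5 dB better is then Φ(−5/SD): 4.8%, 15.9%, 23.8% and 30.9% for SD 3, 5, 7 and 10 dB. The documents give no such SD. The figure matters only for recovered patients at 20 dB or above, whose share is also not given, so it does not convert into a patient count.

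**The case against.** **Raised references are mostly dealt with elsewhere.** SAP 6.12.1 drops the other ear as reference when it already had a loss. Against an old audiogram of the same ear, the patient would have to hear at least 5 dB better than before the episode. This stands as a reason to expect few cases. It does not close the gap: no dB level defines an existing loss, and the 5 dB rule is expressly carried over to old audiograms and norms.

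**Similar is a symmetric word.** A two-sided tolerance is its literal reading, and a one-sided rule changes the meaning to not worse by 5 dB or more. An ear better than a population norm may still be short of its own earlier hearing. That is a fair cost of the change, but a minor one: the written rule already credits ears close to the norm or slightly worse than it.

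**The SAP uses absolute for signed quantities.** SAP 6.2.15 describes change from baseline in absolute terms as a plain subtraction. On a signed reading the problem disappears. But that section defines only change from baseline, not a difference between ears. Signs are also unreliable nearby: SAP 6.12.5.2 writes marked improvement as post-baseline minus baseline above 30 dB, which taken literally is worsening.

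**Stronger readings to avoid.** A reader might infer that every ear 5 dB better than its reference is counted as a failure, or that the best outcomes are lost. The documents do not support this: the limbs are joined by or, so every ear below 20 dB is recovered whatever the reference. A reader might also want to attach a percentage of patients. The documents give no distribution of reference PTA or of between-ear differences, so any such figure would be a guess.

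**Conclusion.** On the ordinary reading of an absolute difference, the rule is non-monotone and misclassifies a defined group: affected-ear PTA of 20 dB or above, reference of 25 dB or above, and the affected ear at least 5 dB better. Nobody below 20 dB is touched. Under the definition in Protocol 6.2.3, which has no similarity limb, the issue does not arise.

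The size cannot be derived from the documents and is probably small. The rule is the same in every arm. The endpoint is analysed descriptively in the ITT set and lies outside the testing order of SAP 6.12.6, so the primary analysis, alpha and power are unaffected. This is a desirable correction, not a necessary one.

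**What to change.** In SAP 6.12.5.1, define similarity as affected-ear PTA minus reference PTA below 5 dB, with the order of subtraction written out. Because the recovery table (14.2.3.1a) is checked by independent programming, both programmers would then work from one unambiguous rule. The change needs no new data and can only reclassify ears at least 5 dB better than their reference.

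The cost is the shift in meaning already noted: an ear better than an old audiogram or an ISO norm is credited as recovered even if its hearing before the episode was better still. Tabulating the recovery proportion by reference type would show how much rests on this. SAP 6.12.2 already tabulates reference type by treatment group, so the variable is available.

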**6.12.5.2 % of patients with marked improvement defined as PTA threshold absolute improvement > 30 dB**

The proportion of patients with marked improvement in pure tone audiometric air conduction testing (average of the hearing threshold of 3 contiguous most affected hearing frequencies in decibels as identified at study entry), that is, PTA at post-baseline minus baseline PTA is > 30dB, will be summarized by treatment group for Day 28 and Day 84 along with an exact confidence interval.

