### 2. Calculation of overall TFI score

- (1) Sum all valid answers from both TFI pages (maximum possible score = 250 if the respondent were to rate all 25 TFI items at the maximum value of 10).
- (2) Divide by the number of questions for which that respondent provided valid answers (yields the respondent's mean item score for all items having valid answers).
- (3) Multiply by 10 (provides that respondent's overall TFI score within 0-100 range).

**CAUTION—**Overall TFI score is not valid if respondent omits **7 or more items**. To be valid as a measure of tinnitus severity, the respondent must answer **at least 19 items** (76% of items).

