### 6.2.15 Change from baseline

Change from baseline in absolute terms is defined as the baseline value subtracted from the postbaseline value.

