- Tinnitus numeric rating scale (NRS) as recorded in the eCRF (XT.XTCAT=“Questionnaire”): score (from 0 to 10)
- Vertigo NRS: score (from 0 to 10)
- Speech recognition threshold (SRT) on affected ear: minimum hearing level at which the patient can correctly recognizes 50 % of the presented speech material
- Word recognition score (WRS) also called Speech discrimination score on affected ear: percentage of words correctly repeated at 60dB and 80dB
- Tinnitus functional index (TFI) Total Score (from 0 to 250)

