### 6.12.2 Primary Efficacy Analysis

	Sponsor:	Sensorion
	Protocol Number:	SENS 401-201
STATISTICAL ANALYSIS PLAN. PHASE 2-3-4		

The null and alternative hypotheses for part 1 of the study are as follows, where  $\mu_H$ ,  $\mu_L$  and  $\mu_P$  are defined as the mean change in PTA of the high dose, low dose, and placebo respectively:

$H_{0H}: \mu_H - \mu_P = 0$ ,  $H_{AH}: \mu_H - \mu_P < 0$  (greater decrease on high dose)

$H_{0L}: \mu_L - \mu_P = 0$ ,  $H_{AL}: \mu_L - \mu_P < 0$  (greater decrease on low dose)

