***6.12.5.8 Tinnitus burden based on the change in tinnitus QOL scores at day 1,7,14, 28 and 84***

The Tinnitus Functional Index (TFI) comprise of 25 questions on the impact of the tinnitus on the individual behavior and feelings in which items 1 and 3 are in percentage scale, that is, from 0 to 100 with increment of 10 while all the other items are in 0 to 10 scale with an increment of 1. Thus, items 1 and 3 need to be transformed into a 0 to 10 scale by dividing the value by 10 before obtaining the subscale score to which the items belong, as well as the total TFI score. The questionnaire has eight subscales that address the intrusiveness of tinnitus (items 1, 2, 3), the sense of control the patient has (items 4, 5, 6), cognitive interference (items 7, 8, 9), sleep disturbance

	Sponsor:	Sensorion
	Protocol Number:	SENS 401-201
STATISTICAL ANALYSIS PLAN. PHASE 2-3-4		

(items 10, 11, 12), auditory issues (items 13, 14, 15), relaxation issues (items 16, 17, 18), quality of life (items 19, 20, 21, 22), and emotional distress (items 23, 24, 25). In obtaining the subscale score, the response to all the items that belong to the corresponding subscale score will be added then divided by the number of items that have responses, and eventually multiplied by 10. Thus, the subscale score would range from 0 to 100. For a valid subscale score, no more than 1 item should have missing response. Otherwise, the subscale score will be set to missing. The TFI total score is obtained by adding the values of all the items that have responses then dividing by the number of items that have responses, and eventually multiplying by 100. TFI total score will range from 0 to 100. For a valid TFI total score, there should be at least 19 items that have non-missing responses. Otherwise, the TFI total score will be set to missing.

The TFI subscale scores and total score, along with the corresponding changes from baseline will be summarized for all the relevant timepoints by treatment group. All responses to TFI items, as well as derived TFI data (total and subscale scores) will be listed.

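### Two SAP derivation rules give wrong values if followed: marked improvement has its sign reversed, and the TFI total is multiplied by 100 instead of 10

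*SAP*

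**What the plan says.** **Marked improvement.** The heading of SAP 6.12.5.2 gives the endpoint as "marked improvement defined as PTA threshold absolute improvement > 30 dB", and protocol 6.2.3 lists the percentage "of patients with marked improvement defined as PTA absolute improvement > 30 dB". The body of SAP 6.12.5.2 then spells out the derivation as "PTA at post-baseline minus baseline PTA is > 30dB". Two other parts of the SAP fix the direction:

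- SAP 6.2.15: "Change from baseline in absolute terms is defined as the baseline value subtracted from the postbaseline value".
- SAP 6.12.2, alternative hypothesis for the high dose: "greater decrease on high dose".

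**TFI total.** SAP 6.12.5.8 puts all items on a 0 to 10 scale, sums them, divides by the number answered, and ends with "eventually multiplying by 100. TFI total score will range from 0 to 100". Protocol Appendix 1 uses the same sum and division but multiplies by 10, giving the "overall TFI score within 0-100 range". SAP 6.7.2 lists the baseline variable as "Tinnitus functional index (TFI) Total Score (from 0 to 250").

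**The concern.** Each rule conflicts with text around it, and in each case the explicit formula is the wrong part.

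For marked improvement, a positive post-minus-baseline difference in a threshold is a loss of hearing. If the clause is programmed as written, the more an arm restores hearing, the fewer patients it will show as markedly improved.

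For the TFI, programming the multiplier as written makes totals and changes in total ten times too large. They would not be comparable with the eight subscales, which SAP 6.12.5.8 correctly multiplies by 10, or with the 0 to 100 scale in the protocol. A baseline table on 0 to 250 could not be matched to the efficacy table for the same score.

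SAP Section 8, which lists departures from the protocol, mentions neither rule, so neither reads as a deliberate change.

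**Working it through.** **1. Sign of the marked-improvement rule**

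Inputs: protocol 10.1.1 defines the threshold as the lowest level the patient can hear, so fewer dB means better hearing. Change is post-baseline minus baseline (SAP 6.2.15), and benefit is a negative change (SAP 6.12.2).

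- Written rule: post − baseline > 30.
- Rule implied by the heading: baseline − post > 30, that is, post − baseline < −30.

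| Baseline → post (dB) | Post − baseline | Written rule | Rule in heading |
|---|---|---|---|
| 90 → 50 | −40 | not counted | counted |
| 100 → 30 | −70 | not counted | counted |
| 50 → 90 | +40 | counted | not counted |
| 60 → 95 | +35 | counted | not counted |

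The word *absolute* in the heading does not rescue the clause, because the clause states a signed difference without a modulus.

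**2. Effect on reported percentages (illustration)**

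The documents give no expected mean change per arm, so the means below are assumptions. The change is taken as normal with SD 30 dB, the Part 1 planning value (protocol 13.1, SAP Section 4).

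- Written rule: P(change > 30) = 1 − Φ((30 − mean)/30).
- Rule in heading: P(change < −30) = Φ((−30 − mean)/30).

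| Assumed mean change (dB) | Written rule | Rule in heading |
|---|---|---|
| 0 | 16% | 16% |
| −10 | 9% | 25% |
| −20 | 5% | 37% |
| −30 | 2% | 50% |
| −40 | 1% | 63% |

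With the Part 2 planning SD of 20 dB and a mean change of −20 dB, the two rules give 0.6% and 31%. The pattern does not depend on the SD: the written rule falls as recovery improves, while the stated endpoint rises.

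There is also a ceiling. The imputation code in SAP 6.12.3 caps PTA at 120 dB. If that cap is taken as the top of the scale, a patient with a baseline of 90 dB or more cannot worsen by more than 120 − 90 = 30 dB, and so could never meet the written rule.

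**3. TFI total**

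Formula: (sum of answered items ÷ number answered) × multiplier. The SAP states a range of 0 to 100, so the maximum is the test.

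- 25 items at 10: sum 250, mean 10. With ×100 the total is 1000; with ×10 it is 100.
- 19 items at 10 (the minimum for a valid total): mean 10. Again 1000 and 100.
- 25 items at 5: sum 125, mean 5. With ×100 the total is 500; with ×10 it is 50; the plain sum is 125.

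The stated 0 to 100 range is not reproduced by ×100, which gives 0 to 1000. It is reproduced exactly by ×10. The 0 to 250 range in SAP 6.7.2 matches the unaveraged sum, which is step 1 of the protocol's scoring instructions and not the total score.

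**The case against.** The best counter-argument is that these are drafting slips whose meaning is plain. The heading of 6.12.5.2, SAP 3.3 and the protocol all say improvement. The sentence after the TFI formula gives the right range, and no programmer can satisfy both ×100 and 0 to 100. The SAP contains no program for either endpoint, so nothing shows that a wrong value was or will be derived. Both endpoints are presented descriptively in the ITT set (SAP 6.12.5) and neither is in the testing order of SAP 6.12.6. The TFI error is a constant factor of 10, so it cannot change direction, ranking or a standardised difference. Only two TFI ranges are actually stated; the 0 to 1000 scale is what the formula implies. The tables are independently programmed, and the correctly worded 10 dB responder table would expose the sign error, since every patient flagged by the written rule would be a non-responder at that visit.

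All of this limits the consequences, and the limits are accepted. It does not remove the contradiction. Independent programming checks agreement between two programmers working from one specification. If both follow the explicit formula, they agree on the wrong answer. If they resolve the conflict differently, the choice is made once data are available.

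**Conclusion.** The point holds. As written, SAP 6.12.5.2 selects patients who worsened by more than 30 dB, the opposite of its heading, and SAP 6.12.5.8 produces a total of 0 to 1000, ten times its stated range. SAP 6.7.2 adds a second stated range for the same score.

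The sign error is the more serious, because it reverses the meaning of the table; the TFI error only rescales. Harm arises only if the text is programmed literally. The examples and the TFI arithmetic need no assumptions. The percentages are illustrative and rest on the assumed means, normality and the planning SDs. Primary and secondary analyses, multiplicity control, power and sample size are unaffected. The SAP should be corrected, but the error does not threaten the trial's main conclusion.

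**What to change.** Three edits to the SAP:

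- **6.12.5.2:** define marked improvement as *baseline PTA minus post-baseline PTA > 30 dB*.
- **6.12.5.8:** change the multiplier for the TFI total from 100 to 10.
- **6.7.2:** give the range of the baseline TFI total as 0 to 100.

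The corrected text should be in place before Tables 14.2.3.2a and 14.2.3.8a and their Part 2 counterparts are finalised, and any existing programs for these two endpoints and the baseline TFI table should be checked against it. The 10 dB responder rule in 6.12.5.4 is worded as an improvement and needs no change. The cost is three wording corrections; no data collection, analysis model or clinical rule changes.
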